9.2.1. Suspected Drug-Induced Liver Injury

The number and percentage of patients with at least one post-baseline abnormal liver function test will be presented. A listing of patients who have abnormal liver function tests and meet DILI criteria will be provided, including the patient ID, visit, collection date, DILI parameters (ALT, AST, BILI, INR, LDH, CPK) and criteria. Abnormal liver function tests are defined as liver test values that meet at least one of the criteria listed below:

Liver Chemistries that trigger Drug-Induced Liver Injury (DILI) investigation:

- Transaminases (ALT or AST ≥ 3 x baseline or 500 U/L, whichever comes first) AND bilirubin (total bilirubin > 2 x ULN) elevations.
- Transaminase elevations alone (ALT or AST > 10 x ULN or 5 x baseline or absolute threshold of 800 U/L, whichever comes first) in the presence of normal LDH and CPK.
- Total bilirubin increased, unrelated to hemolysis (elevated reticulocyte count) or established genetic diseases, such as Gilbert's syndrome:
 - Doubling if total bilirubin was < 3 mg/dL (equivalent to 51.3 $\mu\text{mol/L}$) at baseline OR
 - Increase by > 3 mg/dL (equivalent to 51.3 $\mu\text{mol/L}$) if total bilirubin was ≥ 3 mg/dL (equivalent to 51.3 $\mu\text{mol/L}$) at baseline.
- INR increase refractory to vitamin K administration.
 - Increase by > 1.5 if INR was normal at baseline OR
 - Increase by > 0.4 if INR was abnormal at baseline.
- Any increase in total bilirubin and transaminases if accompanied by EITHER a symptom of clinical hepatitis (e.g., vomiting, nausea, right upper quadrant pain) OR immunological reaction (rash or $> 5\%$ eosinophilia)

Below six eDISH plots (maximum ALT/AST with concurrent TBL) will be presented:

- Total bilirubin (in xULN) versus maximum post-baseline ALT (in xULN) for participants with baseline ALT \leq ULN;
- Total bilirubin (in xULN) versus maximum post-baseline AST (in xULN) for participants with baseline AST \leq ULN;
- Total bilirubin (in xBaseline) versus maximum post-baseline ALT (in xBaseline) for participants with baseline ALT $>$ ULN;
- Total bilirubin (in xBaseline) versus maximum post-baseline AST (in xBaseline) for participants with baseline AST $>$ ULN;
- Total bilirubin (in xULN) versus maximum post-baseline ALT (in xBaseline) for participants with baseline ALT $>$ ULN;

- Total bilirubin (in xULN) versus maximum post-baseline AST (in xBaseline) for participants with baseline AST > ULN

The individual graphs (ALT, AST, TBL, and ALP) (xULN vs Study Days) for any participants meeting the DILI criteria or participants with TEAEs related to ALT/AST and other Hepatic Enzyme Elevations will be presented. Study day based on the date of planned single dose will be used.

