7.2.2 Inclusion Criteria

Patients meeting all of the following criteria will be considered eligible for enrollment in the study:

Diagnosis and Criteria for Inclusion:

1. Adults between 18 and 75 years of age (inclusive).

2. Have a clinical diagnosis of large-duct PSC with evidence of more than 6 months duration with either a consistent MRCP or ERCP showing sclerosing cholangitis and historical evidence of elevated ALP.
3. Willing to sign informed consent.
4. Women of childbearing potential (WOCBP) and males with female partners of childbearing potential must agree to use contraception as detailed in [Section 9.3.18](#). Women of nonchildbearing potential (WONCBP) must meet the definition in [Section 9.3.18](#) and have a confirmatory FSH level ≥ 40 mIU/mL.
5. ALP value $> 1.5 \times \text{ULN}$ but $\leq 10 \times \text{ULN}$ at Visit 1 (Screening). Before starting 12 weeks treatment variability of $< 30\%$ between ALP values at Visit 1 and Visit 2 must be confirmed. If variability is $> 30\%$ a third ALP value may be obtained. If the third ALP value meets $> 1.5 \times \text{ULN}$ but $\leq 10 \times \text{ULN}$ the patient can start the 12-week treatment period.
6. Arms 1-3 Only: Total bilirubin $< 1.5 \times \text{ULN}$ (unless due to Gilberts Syndrome or hemolysis) and normal direct bilirubin.
7. AST and ALT $\leq 5 \times \text{ULN}$
8. Serum bile acid level $> \text{ULN}$
9. Arms 1 - 3 Only: An MRCP or equivalent imaging modality performed within 6 months before the Screening Period that is consistent with PSC without a CRS,
10. Arm 4 Only: An MRCP or equivalent imaging modality performed within 6 months before the Screening Period that is consistent with PSC with a CRS, or clinically relevant bile duct obstruction (see Inclusion # 12 for additional information).
11. Use of UDCA with a total daily dose ≤ 23 mg/kg/day, or bile acid-binding resins are permitted, with a minimum of 3 months of stable treatment prior to the Screening Period, and expected to remain on a stable dose through the 12-week treatment period; or a minimum of 3 months off UDCA prior to the Screening Period if UDCA was recently discontinued.

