9.3.6 Individual Patient Safety Monitoring

9.3.6.1 Liver Monitoring

Strategies to monitor markers of liver disease throughout the study are outlined below where the ULN will be based on central laboratory reference values. To make the distinction among the type of injury, and to make a causality assessment, the Roussel Uclaf Causality Assessment Method ([Appendix 2](#)) will be used.

For abnormalities classified as hepatic adverse events and/or hepatic decompensation, a PK sample should be collected as close to the onset of the event as possible.

If isolated transaminase elevations are observed, defined as:

Normal bilirubin AND absence of clinical hepatitis symptoms AND

- ALT or AST $\geq 5 \times$ ULN (if normal at baseline) OR
- ALT or AST $\geq 3 \times$ baseline (if abnormal at baseline) or > 500 U/L, whichever comes first

Then:

- a. Repeat liver profile (AST, ALT, bilirubin, and prothrombin time [PT] or INR) within 2 to 3 days
- b. Evaluate creatine phosphokinase (CPK) and lactate dehydrogenase (LDH)
- c. As needed (for example, persistent ALT/total bilirubin elevation or worsening of liver function), consider evaluation for alternative etiologies

Monitor the patient using the close observation guidelines found below.

If any ONE of the following criteria are met:

1. Transaminases (ALT or AST $\geq 3 \times$ baseline or 500 U/L, whichever comes first) AND bilirubin (total bilirubin $> 2 \times$ ULN) elevations
2. Transaminase elevations alone (ALT or AST $> 10 \times$ ULN or $5 \times$ baseline or absolute threshold of 800 U/L, whichever comes first) in presence of normal LDH and CPK
3. Total bilirubin increased, unrelated to hemolysis (elevated reticulocyte count) or established genetic diseases, such as Gilbert's syndrome

- a. Doubling if total bilirubin was < 3 mg/dL (equivalent to $51.3 \mu\text{mol/L}$) at baseline
OR
 - b. Increase by > 3 mg/dL (equivalent to $51.3 \mu\text{mol/L}$) if total bilirubin was ≥ 3 mg/dL (equivalent to $51.3 \mu\text{mol/L}$) at baseline
4. INR increase refractory to vitamin K administration
- a. Increase by > 1.5 if INR was normal at baseline OR
 - b. Increase by > 0.4 if INR was abnormal at baseline
5. Any increase in total bilirubin and transaminases if accompanied by EITHER a symptom of clinical hepatitis (e.g. vomiting, nausea, right upper quadrant pain) OR immunological reaction (rash or $> 5\%$ eosinophilia)

Then:

- a. Interrupt study medication

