- b. Initiate drug-induced liver injury work-up for alternative etiologies
- c. Repeat liver profile (AST, ALT, total bilirubin, direct bilirubin) and PT or INR within 48 to 72 hours
- d. Monitor the patient using the close observation guidelines found below.

Close Observation

For patients requiring closer observation:

- Repeat liver enzyme and serum bilirubin tests two or three times weekly.
Frequency of re-testing can decrease to once a week or less if abnormalities stabilise or the study drug has been discontinued and the patient is asymptomatic
- Obtain a more detailed history of symptoms and prior or concurrent diseases
- Obtain a history of concomitant drug use (including non-prescription medications and herbal and dietary supplement preparations), alcohol use, recreational drug use, and special diets
- Consider ruling out alternate etiology including acute viral hepatitis types A, B, C, D, and E; autoimmune or alcohol-associated liver disease; non-alcoholic steatohepatitis (NASH); hypoxic/ischemic hepatopathy; and biliary tract disease
- Obtain a history of exposure to environmental chemical agents
- Obtain additional tests to evaluate liver function, as appropriate (e.g. INR, direct bilirubin)
- If the Roussel Uclaf Causality Assessment Method (RUCAM) scoring meets DILI criteria, the patient must be discontinued from the study drug.

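### The SAP DILI count omits an ALT/AST-only rise of any size if LDH or CPK is abnormal, and with mildly raised bilirubin neither protocol liver-monitoring tier applies

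*SAP*

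**What the plan says.** SAP 9.2.1 sets the rule for the table: "Abnormal liver function tests are defined as liver test values that meet at least one of the criteria listed below". The same criteria govern the listing: "A listing of patients who have abnormal liver function tests and meet DILI criteria will be provided". There are five:

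1. ALT or AST at least 3 x baseline or 500 U/L, "AND bilirubin (total bilirubin > 2 x ULN) elevations".
2. ALT or AST alone: above 10 x ULN, 5 x baseline, or an "absolute threshold of 800 U/L, whichever comes first) in the presence of normal LDH and CPK".
3. Total bilirubin doubled (baseline below 3 mg/dL) or up by more than 3 mg/dL (baseline 3 mg/dL or above), not explained by hemolysis or a genetic condition.
4. INR rise that does not respond to vitamin K.
5. Any rise in both bilirubin and transaminases with hepatitis symptoms, rash or eosinophilia.

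Protocol 9.3.6.1 uses the same five criteria to interrupt drug and start a DILI work-up. Its criterion 2 has the same ending: "absolute threshold of 800 U/L, whichever comes first) in presence of normal LDH and CPK". A lower tier (repeat tests, then close observation) has no LDH/CPK condition, but its entry line reads "Normal bilirubin AND absence of clinical hepatitis symptoms AND" followed by the ALT/AST thresholds. Under close observation, if RUCAM "scoring meets DILI criteria, the patient must be discontinued from the study drug".

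Protocol 7.2.2, inclusion 6, admits patients to Arms 1-3 with total bilirubin below 1.5 x ULN ("unless due to Gilberts Syndrome or hemolysis) and normal direct bilirubin"). It sets no bilirubin limit for Arm 4.

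**The concern.** In criterion 2 the bracket closes before the LDH/CPK condition, so the condition governs all three transaminase thresholds. The other four criteria each need a bilirubin, INR, symptom or immunological change. A very large ALT or AST rise can therefore miss all five criteria because LDH is slightly above its upper limit.

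Two things are at stake. The SAP table can show no abnormal liver tests beside such a rise, in a trial whose primary objective is safety and which is the first exposure of PSC patients to this drug. Also, when bilirubin is mildly raised, the protocol prescribes no follow-up step under either tier.

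**Working it through.** This is a check of rule logic; the plan gives no figure to reproduce. Let A0 and A be ALT (or AST) at baseline and event, and B0 and B total bilirubin at the same times.

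**Rules as written (SAP 9.2.1, Protocol 9.3.6.1)**
- C1: (A >= 3 x A0 or A >= 500 U/L) and B > 2 x ULN
- C2: (A > 10 x ULN or A >= 5 x A0 or A >= 800 U/L) and LDH and CPK both normal
- C3: B >= 2 x B0 if B0 < 3 mg/dL; otherwise B - B0 > 3 mg/dL
- C4: refractory INR rise
- C5: B > B0 and A > A0, with symptoms or immunological reaction
- Lower tier: B <= ULN, no symptoms, and A >= 5 x ULN (normal baseline), or A >= 3 x A0 or > 500 U/L (abnormal baseline)

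**Illustrative cases: ALT 30 x ULN, no symptoms, INR unchanged, CPK normal.** Inclusion 7 caps entry ALT at 5 x ULN, so A/A0 is at least 30/5 = 6. All three cases pass the transaminase part of C2.

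| Case | Bilirubin (x ULN) | LDH (x ULN) | Criteria met | Lower tier | DILI count |
|---|---|---|---|---|---|
| A | 0.8 to 1.0 | 1.05 | none | yes | 0 |
| A | 0.8 to 1.0 | 0.99 | C2 | yes | 1 |
| B | 0.9 to 1.4 (1.4/0.9 = 1.56 x baseline) | 1.05 | none | no | 0 |
| B | 0.9 to 1.4 | 0.99 | C2 | no | 1 |
| C | 1.4, unchanged | 1.05 | none | no | 0 |

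Case B gives the same result for baseline ALT of 0.8, 1, 2, 3 and 5 x ULN (37.5, 30, 15, 10 and 6 x baseline at the event). In case C the patient is in the gap with no bilirubin change at all.

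**Absolute units, with LDH or CPK abnormal.** Assumed ULNs, which the documents do not give: ALT 40 U/L, bilirubin 1.2 mg/dL. ALT rises from 80 to 1000 U/L (12.5 x baseline) or to 4000 U/L (50 x baseline), with the same result for both.

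| Bilirubin (mg/dL) | At event, x ULN | x baseline | Result |
|---|---|---|---|
| 0.8 to 0.8 | 0.67 | 1.00 | lower tier only, count 0 |
| 0.8 to 1.5 | 1.25 | 1.88 | neither tier, count 0 |
| 1.0 to 1.9 | 1.58 | 1.90 | neither tier, count 0 |
| 1.6 to 2.3 | 1.92 | 1.44 | neither tier, count 0 |
| 0.5 to 1.3 | 1.08 | 2.60 | C3 met, counted |
| 1.6 to 2.5 | 2.08 | 1.56 | C1 met, counted |

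With LDH and CPK normal, every row meets C2.

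**Width of the no-tier range.** Let b = B0/ULN and x = B/ULN, with B0 below 3 mg/dL. The lower tier is missed if x > 1, C1 is missed if x <= 2, and C3 is missed if x < 2b. So the range is 1 < x <= 2 with x < 2b:
- b at or below 0.5: no gap, since any value above ULN is a doubling
- b = 0.6: above 1 to below 1.2
- b = 0.75: above 1 to below 1.5
- b = 0.9: above 1 to below 1.8
- b = 1.0: above 1 to below 2.0
- b above 1: above 1 up to and including 2.0

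**With the LDH/CPK condition removed,** the rows in the second table that met no criterion meet C2 and are counted.

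**The case against.** The SAP reproduces the protocol trigger, and a count of patients who met that trigger is a legitimate output. The LDH/CPK condition presumably screens out muscle injury, and a wider count would let some of that in. Little is hidden in a trial of about 24 patients. The eDISH plots and graded listings show the value, and individual graphs also appear for anyone with a hepatic-enzyme TEAE. Investigators can stop drug for a related AE or choose closer observation, related serious or severe events trigger the stopping rules, and the SRC reviews accumulating data. The scenario is a narrow conjunction, and repeat testing gives further chances of a sample with normal LDH and CPK. Finally, the lower tier's bilirubin condition does not say total, and Arms 1-3 patients enter with normal direct bilirubin.

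Most of this is right about consequence and leaves the rule unchanged. The other outputs do not supply a count: shift tables use only low, normal and high, so a rise from 5 to 30 x ULN reads as high to high, and CTCAE grades appear only in listings. Investigator discretion is not a defined step. Neither document states a muscle-injury rationale, and the condition is not limited to CPK. The close-observation list repeats liver enzymes and bilirubin but does not name LDH or CPK. The direct-bilirubin reading lacks support: the lower tier's own follow-up step refers to total bilirubin, as do criteria 1 and 3. Even on that reading the SAP count stays at zero.

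**Conclusion.** The concern holds. An ALT/AST rise of any size that meets only criterion 2's transaminase part is left out of the SAP DILI count and listing if LDH or CPK is abnormal at every qualifying sample. If total bilirubin is also above ULN, not above 2 x ULN and less than doubled, without symptoms, neither protocol tier applies. With normal bilirubin and no symptoms, the lower tier still gives repeat tests, close observation and the RUCAM stopping rule, but not automatic interruption.

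The conclusion rests on a literal reading of criterion 2 and on normal bilirubin meaning total bilirubin. The results in multiples of ULN do not depend on the assumed ULNs, provided baseline bilirubin is below 3 mg/dL. The documents give no frequency and the case may be rare; one patient is 1 of 6 in an arm (17%). The TEAE primary endpoint is unaffected and the values stay visible elsewhere. This should be corrected, but it does not undermine the trial.

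**What to change.** **SAP 9.2.1.** Count and list every patient with ALT or AST above 10 x ULN, at 5 x baseline or at 800 U/L, regardless of LDH and CPK. Add a sub-row for those with both normal, which preserves the protocol trigger and the current figure. Show baseline LDH and CPK beside the event values already planned for the listing.

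**Protocol 9.3.6.1.** State that any ALT/AST rise over the criterion 2 thresholds with abnormal LDH or CPK gets at least close observation, whether or not bilirubin is normal. Whether it should also interrupt drug is the sponsor's clinical decision.

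**Cost.** The SAP change is one sentence and one table row, from chemistry already collected. A few rises of muscle origin will enter the wider count; the CPK column identifies them and the sub-row excludes those with abnormal CPK. The protocol clause needs an amendment. Because the SAP already cites a March 2025 drug dictionary against a planned study period of 2022-2025, that clause may come too late for enrolled patients. The SAP change is worth making in any case.

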9.2.2. Faecal Calprotectin Assessment

For patients with IBD, stool samples will be collected (at home) prior to each study visit for assessment of faecal calprotectin. Faecal calprotectin assessments are performed at visits indicated in [Table 2](#).

Summary table of observed values, relative and absolute change from baseline 1 to each post-baseline visit and the last visit will be presented in the Safety analysis set. The 2-sided 95% CI of the mean for relative and absolute change from baseline 1, and observed values will be presented along with descriptive statistics. Baseline 1 is defined as assessment performed on the day of the planned single dose. Supporting listing will also be presented for the Safety Analysis Set.

9.3. Vital Sign Measurements

Summary tables will be presented by treatment for vital sign data, including height (cm), weight (kg), pulse rate (PR) (beats/min), systolic blood pressure (mmHg), diastolic blood pressure (mmHg), and temperature (°C) in the Safety analysis set. Observed results and absolute change from baseline 1 to each post-baseline time point and the last visit will be presented. Change from baseline 1 will only be calculated for patients having non-missing baseline 1 and post-baseline measurements. The height assessment will only be done at the Screening visit. All vital signs data will be presented in a listing.

Abnormal vital sign values are defined as post-baseline values that meet one of the criteria listed below if baseline 1 values are normal, or post-baseline values that worse than the baseline value if baseline 1 values are abnormal. The number and percentage of patients with at least one post-baseline abnormal vital sign value will be presented. The shift table in categories (Low, Normal, High) for the minimum and maximum post baseline values will be presented for each vital sign parameter. This will also be repeated for each timepoint according to the Schedule of Assessment. A supportive listing of patients with abnormal post-baseline values will be provided including the patient ID, baseline 1, post-baseline values and criteria.

Abnormal vital sign values will be presented based on the following criteria:

- Systolic blood pressure (mmHg):
 - Normal - ≥ 90 and ≤ 140
 - Low - < 90
 - High - > 140
- Diastolic blood pressure (mmHg):
 - Normal - ≥ 50 and ≤ 90
 - Low - < 50
 - High - > 90
- Pulse rate (beats/min):

- Normal - ≥ 50 and ≤ 120
- Low - < 50
- High - > 120

9.4. Physical examination

A physician or suitably trained qualified assistant will perform a complete physical examination at times presented in Table 2. A complete physical examination will include assessment of general appearance, eyes, ears, nose, throat, head/neck/thyroid, lymph nodes, cardiovascular, lungs/chest, abdomen, genitourinary, extremities, skin, musculoskeletal, and neurologic system; any other findings will also be documented.

Physical examination results will be summarised at each visit with percentages and frequencies along with abnormalities by treatment arm. Physical examination and skin assessment data will be listed (including pre-treatment and post-treatment results).

9.5. Electrocardiogram results

Standard resting 12-lead electrocardiograms (ECGs) will be recorded after the patient has been supine and at rest for at least 5 minutes at the times indicated in the Schedule of Assessments and when judged to be clinically appropriate. The investigator (or designee) will perform a clinical assessment of each 12-lead ECG. The PR, RR, QT and QTcF intervals; QRS duration; and heart rate will be presented.

An overall 12-lead ECG interpretation (Normal, Abnormal Not Clinically Significant, Abnormal Clinically Significant) will be available based on central reading of ECG data. Shifts from baseline 1 to each scheduled post-baseline time point will be presented to show the number and percentage of patients in each category by treatment for patients in the Safety Analysis Set.

A shift table for ECG interpretation will present the shift from baseline 1 to each post-baseline assessment. Patients will be summarised by treatment arms.

Descriptive statistics for observed values at each time point and absolute changes from baseline 1 will be summarised for heart rate (beats/min), PR interval (msec), RR Interval (msec), QRS duration (msec), QT interval (msec), corrected QT interval based on Fridericia's formula (QTcF) (msec) at each scheduled visit. ECG interpretation results (normal; abnormal not clinically significant; abnormal clinically significant) will be presented as the number and percentage of patients in each category at scheduled visits. Patients will be summarised by treatment arm.

All ECG results will be presented in a listing.

9.6. Episodes of cholangitis requiring Antibiotic use

A summary table of the patients with episodes of cholangitis requiring antibiotic use in the 12 weeks prior to single dosing versus the 12-week treatment period will be presented for the Safety Analysis Set. Baseline 1 is defined as data collected on the day of the planned single dose, which are assessments of 12 weeks prior to Single Dosing. Supporting listing will also be presented for the Safety Analysis Set.

